7.6.4 Vital Signs

Individual vital sign measurements (systolic BP, diastolic BP and heart rate) will be listed.

7.7 Pharmacokinetics

Analyses of PK data will be performed using the PK dataset. Listings of PK concentrations and AXA of apixaban by time will be provided.

The pharmacokinetics of apixaban using a population PK assessment and the relationship between apixaban exposure, anti-Xa activity and safety and efficacy endpoints are out of the scope of the CSR.

8 CONVENTIONS

8.1 Safety Data Conventions

Except as noted in [Section 7.6](#), and as applicable, safety data will be handled consistent with BMS safety data conventions summarized below. These conventions include descriptions on how to analyze AE data as well as how to handle partial dates, missing dates, and unknown end dates when analyzing safety data.

For the analyses of efficacy and bleeding endpoints, imputation of missing or partial dates for efficacy and bleeding events will follow the convention outlined, but rather than using the hierarchy “first active study medication date, consent date, visit date corresponding to the visit at which the event was reported”, should instead use the following hierarchy

- “first active study medication date, randomization date, consent date” for efficacy and bleeding endpoints other than death
- “last contact date” for death.
-

A. Subject Population

Key Guidelines
All subjects that receive one or more doses of study treatment constitute the population included in the primary safety analysis.
The analysis and reporting of safety data will be performed on an as assigned (open label trials) or as randomized (randomized trials) basis.
Exception: If a subject received the incorrect medication for the entire period of treatment, the subject will be analyzed in the treatment group associated with the incorrect medication.
Important safety events that occur while the subject is on an incorrect treatment will be specifically discussed in the text of the Clinical Study Report.

B. Inclusion of Events in Primary Analysis

Key Guidelines

All adverse events with an onset date during the treatment phase of a study will be included in the primary safety analysis. This analysis strategy conforms to the "treatment -emergent" concept as described in ICH-E9.
 
Adverse events with an onset date prior to the first day of the active treatment phase of a study are not included in the primary safety analysis. This is regardless of the possible continuance of the adverse event into the treatment phase of the study.
 
Pre-existing conditions or adverse events with an onset date prior to the active treatment phase of a study that worsen with regard to intensity (e.g. mild to moderate) or change from unrelated to study medication to unknown relationship or at least possibly related during the treatment phase of a study are included in the primary safety analysis.
 
At a minimum, non-serious adverse events with an onset date on or before the last date of dosing and serious adverse events with an onset date within 30 days of the last date of dosing are included in the primary safety analysis. Depending on the investigational product being researched (e.g. biologics with long half-life, oncology trials, etc.), an extended observational period may be defined for the primary safety analysis - provided the extended period is defined in the analysis section of the protocol.
 
For development programs where the use of a pre-study treatment observational phase is important in determining the baseline status of a subject, baseline subtraction of events should be undertaken as a supplemental analysis. In such cases, this supplemental analysis is to be specified in the analysis plan.

C. Analysis Periods

Key Guidelines

Analysis periods must be defined in the statistical analysis plan. Typical study periods include:
 
• Pre-treatment period - from first visit until initiation of the next study phase.• Baseline period - an observational period before the initiation of active study treatment used to establish a baseline for subjects. This phase is optional as some studies progress from pre-treatment phase to treatment phase.• Treatment period - begins on the first day study treatment (BMS investigational compound or placebo/active comparator) is administered. The duration of the treatment phase is defined in the protocol and includes the length study treatment is administered• Long-term extension period - defined by a protocol as a follow-on period of study treatment administration after a short-term study. This phase begins on the first day of long-term extension dosing.• Post-treatment period - begins the day after the last dose of study therapy. 
Crossover studies have a layer of complexity due to the planned switching of treatment assignments. The various phases of a crossover study are defined during the set-up and initiation of a study. On the day the next study treatment starts, a new treatment phase of the study begins.

D. Selection of Adverse Events for Counting

Key Guidelines

Where a subject has the same adverse event, based on preferred terminology, reported multiple times in a single analysis period, the subject will only be counted once at the preferred terminology level in adverse event frequency tables.

Where a subject has multiple adverse events within the same system organ class in a single analysis period, the subject will only be counted once at the system organ class level in adverse event frequency tables.

When a subject has the same adverse event, based on preferred terminology, reported multiple times in a single analysis period, the following criteria, in order of precedence, will be used to select the event to be included in summary tables:

- Relationship to study medication
- Intensity of event
- Onset date and time

If relationship is not already reported as Not related versus Related by the investigator, the reported categories will be collapsed into these two categories – Not related and Related. Related events will include those reported as certainly, probably, or possibly related to study medication and those of unknown relationship. Related events will take precedence over Not related events in determining the event to include in summary tables.

More intense events will take precedence over less intense events in determining the event to include in summary tables.

Earlier onset date-time events will take precedence over later onset date-time events in determining the event to include in summary tables.

When reporting adverse events by intensity, in addition to providing a summary table based on the event selection criteria detailed above, summary tables will also be provided based on the most intense event during the analysis period - independent of relationship to study medication. For these tables, the following criteria, in order of precedence, will be used to select the event to be included in summary tables:

- Intensity of event
- Onset date and time

E. Medical Dictionary

Key Guidelines

The Medical Dictionary for Regulatory Activities (MedDRA) will be used when reporting adverse events, medical history findings and/or physical examination findings in standard terminology.

Analysis and reporting of MedDRA data will always be performed using the latest version of the MedDRA dictionary in production at BMS.

Unless otherwise requested by a health authority, only the primary MedDRA hierarchy will be used for regulatory submission reports.

MedDRA is an industry standard terminology that is maintained by an external organization. Updates to this dictionary can have significant impact on the analysis and reporting of our clinical data.

The impact of updates implemented during the course of a study must be assessed and documented (e.g. changes in verbatim coding between interim and final databases).

To avoid the potential of multiple codes being assigned to a single verbatim term, whenever data is integrated across multiple versions of MedDRA the data will be recoded, analyzed and reported in the latest version of MedDRA in production at BMS.

When integrated data is recoded, an impact assessment must be performed to reconcile differences in coding between the individual studies and the integrated database.

F. Partial or Missing Adverse Events Data

Key Guidelines

Missing and incomplete data will be processed according to data processing guidelines detailed in the study data review plan. When an analysis must be performed with incomplete or missing data, the following guidelines can be used to derive data for use in the analysis.

Onset Dates

If the onset date for an adverse event is missing or incomplete, an imputed date will be derived to slot the event to an appropriate analysis period. This derived date will not be reported in summary tables or listings. Every effort will be made to determine the actual onset date for the event or to obtain a reliable estimate for the onset date from the investigator.

If an onset date is missing, the derived onset date will be calculated as the first non-missing valid date from the following list (in order of precedence):

- First active study medication date
- Consent date
- Visit date corresponding to the visit at which the event was reported (for non-serious adverse events only)

If a valid non-missing date is not available for any of these dates, the derived onset date will be set to missing.

If an onset date is incomplete, the derived onset date will be calculated using the following algorithm

Calculate a surrogate date as the first non-missing valid date from the following list (in order of precedence):

- First active study medication date
- Consent date
- Visit date corresponding to the visit at which the event was reported (for non-serious adverse events only)

If a valid non-missing date is not available for any of these dates, the surrogate date will be set to missing.

Based on the information provided, set the derived date to the earliest possible date. If only a year is provided, set the derived date to January first of that year. If a year and month is provided, set the derived date to the first day of that month.

If the surrogate date is non-missing then:

If the derived date is equal to or after the surrogate date use the derived date as calculated

If the derived date is prior to the surrogate date and the surrogate date is consistent with the partial data provided for the onset date, use the surrogate date as the derived date

If the derived date is prior to the surrogate date and the surrogate date is not consistent with the partial data provided for the onset date then set the derived onset date to be the latest possible date based on the partial onset date information provided. If only a year is provided, set the derived date to December 31st of that year. If a year and month is provided, set the derived date to the last day of that month.

If the surrogate date is missing (i.e. all three dates used to determine the surrogate date are missing) then use the derived date as determined in section 3-II.

Resolution Dates

Dates will not be derived for missing or partial resolution dates

Intensity

If an adverse event is reported with an unknown intensity, a derived intensity of 0.5 will be used for the event.

The derived intensity will only be used in determining the event to be counted in frequency tables it will not be displayed in listings or tabulations of the data.

G. Laboratory Data Analysis

Key Guidelines

Analyze laboratory safety data using either a Marked Abnormality or a standard toxicity grade approach.

The data analysis plan should outline the approach used and specify the criteria.

The criteria must be pre-defined and consistent for all studies within a program.

Additional laboratory safety analyses (e.g. mean change from baseline) may also be performed and should be consistent throughout a program.

Implausible and improbable laboratory results will be corrected, if appropriate, at the source (i.e. laboratory) of the data.

If a laboratory confirms a result which has been identified as implausible or improbable, the result will be included in the analysis and its impact, if necessary, addressed in the text of the study report.

H. Programming for Death Events Reporting

Key Guidelines

Programming for death events reporting for annual safety reports, investigator brochure updates, etc ..., that is performed on a not reconciled clinical database, must include all death data being collected in the subject CRF.

SAE and subject status are examples of CRF modules to be taken into account for the programming. This list is of course not exhaustive.

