5 STUDY ASSESSMENTS AND PROCEDURES

5.1 Flow Chart/Time and Events Schedule

Table 5.1-1: Screening Procedural Outline ACCL1333 / CV185155			
Procedure	Consent/Screening Visit^a Day -7 to 4±3	Randomization Visit^a Day 1 to 4±3	Notes
Eligibility Assessments			
Informed Consent/Assent	X		Informed consent/assent must be signed prior to initiating any study procedures.
Inclusion/Exclusion Criteria	X	X	
Medical History	X		
Physical Measurements	X		Height, Body Weight, and calculated Body Mass Index
Catheter History	X		
Concomitant Medication Assessment	X	X	Medications taken at the time of signing the informed consent and after signing the informed consent must be recorded on the appropriate CRF page
Safety Assessments			
Full Physical Examination	X		Includes assessment of signs of venous thromboembolism or bleeding.
Vital Signs	X		Heart rate, BP, respiratory rate and temperature
Adverse Events Assessment		X	Collection of SAEs begins after signed consent; Collection of non-serious AE begins after randomization

Table 5.1-1: Screening Procedural Outline ACCL1333 / CV185155			
Procedure	Consent/Screening Visit^a Day -7 to 4±3	Randomization Visit^a Day 1 to 4±3	Notes
Laboratory Tests	X		CBC with platelets, ALT, AST, conjugated bilirubin, serum creatinine, PT (if available), aPTT and INR (Total bilirubin is acceptable if it is normal. Conjugated bilirubin should be obtained if total bilirubin is high). Renal function must be > 30% of normal for age and size. A platelet count ≥ 20 x 10 ⁹ per L must be obtained within 24 hours prior to starting apixaban. Screening labs as part of the standard of care obtained within 1 week prior to signing the informed consent can be used
Laboratory Tests during LP WBC and RBC in CSF	X	X	WBC and RBC in CSF required only once
Pregnancy Test FRP only	X		Negative serum or urine pregnancy test (minimum sensitivity 25 IU/L or equivalent units of HCG) for FRP.
Clinical Drug Supplies			
Dispense Study Drug		X	Study medication must be initiated prior to or within 12 hours of the first dose of asparaginase or by Day 4±3 of induction chemotherapy, whichever is first
Enroll via IVRS	X		
Randomize via IVRS		X	Randomization occurs between Day 1 and 4±3 of planned 3-4 drug systemic induction chemotherapy. Subjects can be enrolled and randomized during the same visit.

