6.2.1 Nonserious Adverse Event Collection and Reporting

The collection of nonserious AE information should begin at randomization for all patients, including the patients randomized to the usual care arm.

Nonserious AEs should be followed to resolution or stabilization, or reported as SAEs if they become serious (see [Section 6.1.1](#)). Follow-up is also required for nonserious AEs that cause interruption or discontinuation of study drug, or those that are present at the end of study treatment as appropriate. All identified nonserious AEs must be recorded and described on the nonserious AE page of the CRF (paper or electronic). Completion of supplemental CRFs may be requested for AEs and/or laboratory abnormalities that are reported/identified during the course of the study.

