6 STUDY PERIODS, TREATMENT REGIMENS AND POPULATIONS FOR ANALYSES

6.1 Study Periods

The term “**Intended Treatment Period**” will refer to the period from day of randomization through Day 29 visit. This period will be the basis for the summaries of efficacy.

The term “**Treatment Period**” will refer to the period from the day of randomization through the end of treatment Day 29 visit or early discontinuation from study (whichever comes first).

The term “**On-treatment Period**” will refer to the period from the day of first dose through the last dose of study medication. This period will be the basis for the summaries of apixaban safety only, because only the apixaban arm will have dose information.

The term “**Follow-up Period**” will refer to the period starting the day after the Day 29 visit or early discontinuation to Day 35 days visit.

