7.6 Safety

Safety presentations will be based on the Safety Population during the Treatment Period. In addition to the analyses and summaries based on the Treatment Period, the analyses and summaries for bleeding outcomes, AEs, SAEs, SAEs with death outcome, AEs leading to discontinuation, events of special interest, elevations in liver function tests (LFTs), and decreases in platelet counts will also be performed based on the On-Treatment period for apixaban treated subjects only.

For analyses of events during the Treatment Period, non-serious adverse events will be included in analyses if their onset occurs during the Treatment Period, or within 2 days after the end of the Treatment Period. Serious adverse events will be included in analyses if their onset occurs during the Treatment Period, or within 30 days after the end of the Treatment Period. For analyses of events during the On-treatment Period, events will be included if they occur during the On-treatment period, or within 2 days (non SAE) or 30 days (SAE) after the end of the On-treatment period. All events will be listed.

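### Undated adverse events fall before the Treatment Period in controls but inside it in dosed apixaban subjects whenever consent precedes the randomization day

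*SAP*

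**What the plan says.** **Imputation rule.** SAP 8.1 F handles an AE whose onset is wholly missing: "the derived onset date will be calculated as the first non-missing valid date from the following list". The order is date of first active study drug, date of consent, then, for non-serious events only, date of the visit at which the event was reported. The same three dates form the surrogate date used to complete a partial onset. The section says the derived date exists to place the event in an analysis period.

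**Counting window.** SAP 6.1 defines the Treatment Period as "the period from the day of randomization through the end of treatment Day 29 visit" or early discontinuation. SAP 7.6 bases safety tables on it: "non-serious adverse events will be included in analyses if their onset occurs during the Treatment Period" or in the 2 days after it, with 30 days for SAEs. Nothing is allowed before its start. SAP 8.1 B points the same way: "Adverse events with an onset date prior to the first day of the active treatment phase of a study are not included".

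**Dose dates.** SAP 6.1 restricts on-treatment summaries to apixaban "because only the apixaban arm will have dose information".

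**Collection.** Protocol Table 5.1-1 states: "Collection of SAEs begins after signed consent; Collection of non-serious AE begins after randomization". Protocol 6.2.1 adds: "The collection of nonserious AE information should begin at randomization for all patients, including the patients randomized to the usual care arm".

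**Efficacy and bleeding events.** For these endpoints, other than death, the opening of SAP 8.1 replaces the list with "first active study medication date, randomization date, consent date". Death uses the last contact date. General AEs and SAEs are not given this change.

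**The concern.** The rule treats the same record differently according to arm. A control subject can never satisfy the first item on the list, so consent decides, and consent may precede the period in which events are counted. A dosed apixaban subject always satisfies the first item, and first dose follows randomization. An apixaban subject who was never dosed is handled like a control.

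The AE and SAE tables compare arms on all randomized subjects in an open-label trial. A control subject whose only record of a term is undated can be left out of a table that includes an apixaban subject with an identical record. For non-serious events the result also sits badly with the protocol: the rule dates the event before the sites had begun to collect such events.

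**Working it through.** The plan states no figure on this point, so there is none to reproduce. The check follows the dates through the rules.

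**Inputs**
- Imputation order and partial-date algorithm: SAP 8.1 F.
- Window: opens at randomization (SAP 6.1); closes 2 days (non-serious) or 30 days (SAE) after the Treatment Period ends (SAP 7.6).
- Consent: screening may be up to 14 days before randomization (Protocol Table 5.1-1, footnote a) or on the same day (Protocol 5.1).
- First dose: on or after randomization (Protocol synopsis, Study Design).
- About 500 subjects randomized 1:1 (SAP 5), so 500/2 = 250 per arm.

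**Worked cases** (dates are illustrative)

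| Onset recorded | Consent | Randomized | First dose | Control date | Apixaban date |
|---|---|---|---|---|---|
| missing | 3 Sep | 5 Sep | 5 Sep | 3 Sep, out | 5 Sep, in |
| new year only | 30 Dec | 3 Jan | 3 Jan | 1 Jan, out | 3 Jan, in |
| September only | 28 Sep | 30 Sep | 1 Oct | 28 Sep, out | 30 Sep, in |
| missing | 5 Sep | 5 Sep | 5 Sep | 5 Sep, in | 5 Sep, in |

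In row 2 the control's earliest possible date, 1 January, is after consent and so is kept; it precedes randomization. For apixaban it is before the surrogate (first dose), which fits the recorded year and is used. In row 3 the control takes the consent date, which fits September. For apixaban the surrogate is 1 October, which does not fit, so the last day of September is used.

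**Enumeration.** Day 1 was set to each of 365 dates. Randomization was on Day r = 1 to 7, consent from Day -7 to the randomization day (no Day 0), first dose from the randomization day to Day 7, and true onset from randomization to Day 29, with an on-schedule Day 29 visit.

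- Consent before randomization: 365 × Σ(6 + r)(8 − r)(30 − r) = 365 × 6,720 = 2,452,800 combinations.
- Consent on the randomization day: 365 × Σ(8 − r)(30 − r) = 365 × 756 = 275,940 combinations.

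| Onset recorded | Control out, apixaban in: consent earlier | Control out, apixaban in: same day |
|---|---|---|
| missing | 100% | 0% |
| year only | 96.2% | 0% |
| month and year | 54.3% | 0% |

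The reverse never occurs. The 2-day and 30-day extensions give the same results. A separate grid with consent 0, 1, 3, 7 or 14 days before randomization agrees for wholly missing onsets. With the randomization date inserted, the arms agree in every combination. The percentages weight all allowed dates equally: they show that the asymmetry exists and which way it runs, not how often it will occur.

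**Effect per subject lost**
- 1/250 = 0.4 percentage points off the control rate.
- 13/250 = 5.2%; 12/250 = 4.8%. The common-event table in SAP 7.6.2 takes terms above 5% in either arm, so the term disappears if apixaban also has 12 or fewer.
- Hypothetical equal true counts with one control subject lost: 13 against 12 gives a relative risk of 13/12 = 1.083; 50 against 49 gives 50/49 = 1.020. With none lost it is 1.00.

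**The case against.** The best case on the other side is that SAP 8.1 is generic sponsor text, not meant to be applied to the letter.

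- **Generic text.** Read literally, 8.1 A confines the primary safety analysis to dosed subjects, which would remove every control, and 8.1 C starts a typical treatment period at first dose. SAP 6.1, 6.3 and 7.6 supply the study's own population and period. That is right, but none of them supplies another onset order for AEs. The order in 8.1 F is the only one stated.
- **A fallback only.** The section offers its steps as guidelines, after a data review plan that is not among the documents and after every effort to obtain the real date. This makes the problem rarer; it does not correct the rule.
- **Worsening events.** 8.1 B brings back an event with earlier onset that worsens, or whose relationship to drug changes, during treatment. This rescues some control events but not those that stay the same. Protocol 6 asks for a new entry after such a change, which may carry its own date.
- **One count per term.** 8.1 D counts a subject once per preferred term, so any dated record of the term in the period removes the effect. This limits the size.
- **Collection is not imputation.** The protocol governs when sites collect; the derived date is internal and never displayed. It still decides whether the event is counted.
- **Limited consequence.** The tables are descriptive, all events are listed, and the direction cannot hide a harm of apixaban. All of this stands and keeps the point below the most serious grade.

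**Conclusion.** The concern holds. When consent precedes the randomization day, the stated rule puts a wholly undated control event outside the Treatment Period and the same event in a dosed apixaban subject inside it. Some partial dates behave the same way; no complete list of them is claimed. When consent and randomization fall on the same day there is no effect.

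The conclusion assumes that 8.1 F is applied as written, that the data review plan does not override it, and that the subject has no other qualifying record of the term. The total effect cannot be calculated from the documents and is probably small. It touches only descriptive AE and SAE tables, and it makes apixaban look worse relative to control. It should be corrected because a pre-specified counting rule ought not to depend on arm and the correction is cheap.

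**What to change.** In SAP 8.1 F, place the randomization date ahead of the consent date in both the missing-onset list and the surrogate-date list. Each list then begins "first active study medication date, randomization date, consent date" and ends with the reporting visit for non-serious events. Dosed apixaban subjects are unchanged.

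The cost is one line in each of two lists and the matching programming. There is one small downside. SAEs are collected from consent, so an undated SAE that truly occurred between consent and randomization would be counted as a Treatment Period event. That would then apply to both arms alike, whereas the present rule already does it for dosed apixaban subjects. It should not arise for non-serious events, which are collected only from randomization.
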